#### Then:

1.Administer 0.5ml DTaP-IPV-Hib-Hep B by intra-muscular injection into the upper right anterolateral thigh (aP group) record in source document and in red book

2. Administer 0.5ml DTwP-Hib-Hep B by intra-muscular injection into the upper right antero-lateral thigh (wP group), record in source document and in red book

3. Administer 0.5ml PCV by intra-muscular injection into the upper left antero-lateral thigh record in source document and in red book (both aP and wP groups)

4. Administer 0.5ml IPV by intra-muscular injection into the lower left antero-lateral thigh (wP group), record in source document and in red book

5. Administer Rotavirus vaccine oral drops

6. Issue eDiary login details to parent (or give paper diary), ask parent to login and change password. Demonstrate eDiary (or paper diary) to parents for recording AEs and paracetamol +/-ibuprofen use and check understanding.

7. Issue a digital thermometer and ruler. Explain how to measure and record temperature, local and systemic reactions, AEs (for 7 days post any vaccination) and concomitant medications (for 28 days post vaccination).

8. Issue the parents/ legal guardian with a continuous temperature-monitoring device together with instructions. Fit on the child and demonstrate how to fit, check function and remove device

9. Observe the participant for 15 minutes (or for 30 minutes for participants who have received Comvac5) after vaccination for any significant acute reactions, with appropriate medical treatment readily available in case of anaphylactic reaction. Any AEs occurring during the observation period should be recorded in the source document

10.Issue (only if parent's do not have any) and provide instructions on the use of paracetamol prophylaxis to those whose infant is randomised to receive wP

11. Instruct parent/legal guardians to contact the study team immediately should the infant manifest any signs/ symptoms they perceive as serious or if the infant is admitted to the hospital.

12. Leave with parents/guardians anaesthetic cream (unless spray is to be used), dressing pads and instructions for blood test visit (V5, at 5months).

13. Schedule next visit

14. Study staff complete red book, paperwork in case of no direct data entry and enter onto database

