Those parents/legal guardians who are interested in their child taking part will be able to contact the study team via telephone, email, postal reply slips or the online registration form on the study website. Once an expression of interest has been received the study team will contact the parent/legal guardian to provide further information. If they haven't already received the study information booklet it will be emailed or posted out to them to read at their leisure or they will be directed to the OVG website where it is also available. If the parent/legal guardian is willing for their child to participate an appointment will be made for the first study visit. If there are no concerns regarding eligibility and a parent is interested in participating, a suitable time will be arranged for the first study visit. Eligible children whose parents are interested in the study will be visited at their home address (SOP OVG011: Safety of Research Staff whilst Travelling), by the paediatric study team.

In light of the current COVID-19 pandemic in the UK, the government has advised reducing social interaction between people to help reduce the transmission of the virus in the community. To enable us to follow these recommendations as much as possible during our visits, and therefore minimise the risk to participants and their family/household, we will be following the infection control precautions, as outlined in the Clinical Study Plan.

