## 9.5.3 Visit 3: 56 days post V1 (+14 days)

1. Check Inclusion/ exclusion criteria are still valid

2. Review eDiary or paper diary for AEs/SAEs and prescription medicine since the last visit

3. Record and report any AEs/SAEs that have occurred since the last visit.

4. Issue new eDiary or paper diary and remind parents to measure and record temperature, local and systemic reactions, AEs (for 7 days post any vaccination) and concomitant medications (for 28 days post vaccination).

5. Measure and record axillary temperature

6. Administer 0.5ml DTaP-IPV-Hib-Hep B by intra-muscular injection into the upper right anterolateral thigh (aP group), record in source document and in red book

7. Administer 0.5ml DTwP-Hib-Hep B by intra-muscular injection into the upper right antero-lateral thigh (wP group), record in source document and in red book

8. Administer 0.5ml PCV by intra-muscular injection into the upper left antero-lateral thigh record in source document and in red book

9. Administer 0.5ml IPV by intra-muscular injection into the lower left antero-lateral thigh (wP aroup), record in source document and in red book

10. Administer Rotavirus vaccine oral drops

11. Issue the parents/ legal guardian with a continuous temperature-monitoring device, together with instructions. Fit on the child and demonstrate how to fit, check function

12. Check parent familiar with how to measure and record temperature, local and systemic reactions, AEs (for 7 days post any vaccination) and concomitant medications (for 28 days post vaccination).

13. Observe the participant for 15 minutes after vaccination for any significant acute reactions, with appropriate medical treatment readily available in case of anaphylactic reaction. Any AEs occurring during the observation period should be recorded in the source document

14. Issue (only if parent's do not have any) and provide instructions on the use of paracetamol prophylaxis to those whose infant is randomised to receive wP

15. Instruct parent/legal guardians to contact the study team immediately should they manifest any signs/ symptoms they perceive as serious or if the child is admitted to the hospital.

16. Leave with parents/guardians anaesthetic cream (unless spray to be used), dressing pads and instructions for blood test visit if not given previously.

17. Schedule next visit

18. Study staff complete red book, paperwork in case of no direct data entry and enter onto database

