#### Investigational products:

• DTaP-IPV-Hib- Hep B: Infanrix hexa ® (GSK): is diphtheria (D), tetanus (T), pertussis (acellular component) (Pa), hepatitis B (rDNA) (HBV), poliomyelitis (inactivated (IPV) and *Haemophilus influenza* type b (Hib) conjugated vaccine (adsorbed). The vaccine contains 3 *Bordetella pertussis* antigens: Pertussis Toxoid (PT), filamentous Haemagglutinin (FHA) and pertactin (PRN). The vaccine is indicated for primary and booster to prevent diseases described above and is licensed to be used in the European Union, in children between 6 weeks and 36 months of age. Infanrix-hexa will be administered intramuscular as a 2-dose primary (2 and 4 months) and a booster at 12 months of age as described in the SMPC section 4.2. Infanrix-hexa will also be used as a booster at 12 months for the children primed with DTwP-Hib-Hep B an immovax-IPV. The vaccine will be purchased commercially in single dose prefilled syringe and a vial containing Hib powder, preparation will be done according to section 6.6 of the SmpC.

• **DTwP-Hib-Hep B:** Comvac 5 ® (Bharat Biotech) diphtheria (D), tetanus (T), pertussis (whole cell) (w), hepatitis B (rDNA) (HBV), and *Haemophilus influenza* type b (Hib) conjugated vaccine (adsorbed). Will be given intramuscular as a 2-dose primary (2 and 4 months).

- IPV: Imovax ® polio (Sanofi Pasteur Ltd): Inactivated poliomyelitis vaccine, containing 3 types of the poliovirus: type 1 (Mahoney), type 2 (MEF1) and type 3 (Saukett). Is indicated for infants from 2 months of age, children and adults for both primary and booster doses. This vaccine is licensed in 60 countries including France and Finland. Imovax-polio will be given intramuscular as a 2-dose primary (2 and 4 months). The vaccine will be purchased commercially in single dose prefilled syringes, preparation will be done according to section 6.6 of the SmpC
- PCV13: Prevenar13® (Pfizer Limited): a pneumococcal conjugate vaccine that contains 13 different pneumococcal serotypes (1, 3, 4, 5, 6A, 6B, 7F, 9V, 14, 18C, 19A, 19F and 23F) and is licensed in Europe. It is part of the UK routine schedule at 2, 4 and 12 months of age. This vaccine is only going to be administered at 2, 4 and 12 months of age

Non- Investigational products:

The routine NIP vaccines are not part of this study, but will be given to all infants in the study by the study team for practical reasons.

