## **10.2 Storage of IMP and other vaccinations**

The IMP and other vaccines on the trial will be stored at the study site following the manufactured recommendation and as per existing SOPs. Vaccines will be shipped at +2°C to +8°C to the study site. Upon receipt at the study site, vaccines will be immediately transferred to a +2°C to +8°C to +8°C temperature monitored refrigerator for storage.

The refrigerator will be secure and have controlled access. Cool boxes with an attached thermometer will be used while transporting the study treatment during scheduled visits.

The temperature of the refrigerator is remotely monitored and the site will be informed of any excursions in temperature. In case of temperature deviations, the study vaccines cannot be used and should be quarantined until authorisation to use the vaccine is received from the manufacturers.

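### The 30-minute watch after Comvac5 at Visit 1 drops to 15 minutes at Visit 3, where the wP arm receives Comvac5 again, with no reason given

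*Protocol*

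**What the plan says.** Comvac5 is the whole-cell product (DTwP-Hib-Hep B) used in the wP arm. Section 10.1 fixes its schedule: "Will be given intramuscular as a 2-dose primary (2 and 4 months"). It is therefore given at Visit 1 and Visit 3 and at no other visit.

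- **Visit 1** (9.5.1, vaccination steps, item 9): "Observe the participant for 15 minutes (or for 30 minutes for participants who have received Comvac5) after vaccination".
- **Visit 3** (9.5.3, item 7, wP group): "Administer 0.5ml DTwP-Hib-Hep B by intra-muscular injection into the upper right antero-lateral thigh".
- **Visit 3** (9.5.3, item 13, all infants): "Observe the participant for 15 minutes after vaccination for any significant acute reactions".
- **Visit 3** (9.5.3, item 14), which keeps another wP-specific step: "provide instructions on the use of paracetamol prophylaxis to those whose infant is randomised to receive wP".

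The remaining vaccination visits (2, 4, 6 and 7) also set 15 minutes, but no Comvac5 is given at them. Neither the risk section (9.11) nor the amendment history (Appendix D) mentions observation time.

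**The concern.** The protocol sets a longer watch for one product, then sets a shorter one the next time the same infants receive that product, without saying why. The Visit 1 exception is defined by what the infant received, so a reader would expect it wherever Comvac5 is given.

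The stake is a safety procedure, not inference. Staff who follow 9.5.3 as written will watch wP infants for half the time used after dose 1. This matters somewhat more if vaccination takes place at home, because supervised observation ends when staff leave. Section 9.1 says "Eligible children whose parents are interested in the study will be visited at their home address", and section 10.2 says cool boxes "will be used while transporting the study treatment during scheduled visits". Home vaccination at Visit 3 is a reasonable inference from these, but the protocol does not say so for that visit.

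**Working it through.** No power, sample-size or alpha figure bears on this point. The check is a comparison of the visit instructions, followed by simple arithmetic on the size of the gap.

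**1. Comparison by visit**

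| Visit | Comvac5 given (wP arm)? | Observation stated |
|---|---|---|
| 1 (2 months) | Yes, dose 1 | 15 min; 30 min after Comvac5 |
| 2 | No | 15 min |
| 3 (4 months) | Yes, dose 2 | 15 min, no exception |
| 4 | No | 15 min |
| 6 (12 months) | No | 15 min |
| 7 (13 months) | No | 15 min |

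Comvac5 is given at two visits and the exception appears at one. The Visit 3 line matches the standard line used where no Comvac5 is given, which fits reuse of a template sentence.

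**2. Purpose of the watch**

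Visit 3 item 13 reads: "Observe the participant for 15 minutes after vaccination for any significant acute reactions, with appropriate medical treatment readily available in case of anaphylactic reaction". Visit 1 item 9 states the same purpose. The target is acute and anaphylactic reactions at both doses, so the stated purpose gives no ground for different times.

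**3. Size of the gap**

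The shortfall per wP infant at Visit 3 is 30 - 15 = 15 minutes. The wP arm has 57 infants (Table 1).

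- If all attend Visit 3: 57 x 15 = 855 minutes; 855 / 60 = 14.25 hours.
- If all expected withdrawals occur before Visit 3 (an assumption; section 7.1.2 plans 90 infants in the final analysis, so 90 / 2 = 45 per arm): 45 x 15 = 675 minutes; 675 / 60 = 11.25 hours.

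These figures are the staff time needed to restore the watch, not a measure of harm. The protocol gives no rate of reactions arising between 15 and 30 minutes, so the benefit cannot be quantified from it.

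**4. Effect on endpoints**

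The primary endpoint is PT antibody at 13 months and does not depend on observation time. Adverse events and diary reactions are collected from Day 0 to Day 7 after Visits 1, 3 and 6 in both arms (sections 9.8 and 13.3.1), so the reactogenicity comparison is not materially affected.

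**The case against.** The strongest reply is that the two instructions do not contradict each other. Each visit has its own clear rule, and the difference could be a deliberate first-dose precaution. The background on adverse events says hypotonic-hyporesponsive episodes typically follow the first dose. History of allergy to a vaccine component is an exclusion criterion, and eligibility is re-checked at Visit 3, so a recognised allergic reaction to dose 1 should be caught. The repeated paracetamol step is weak evidence of an omission, because paracetamol was the subject of a separate amendment. Other safeguards apply at Visit 3: treatment at hand, instructions to contact the team immediately, a 24-hour phone line and 24-hour temperature monitoring. The Investigator's Brochure and Clinical Study Plan are not shown and could address observation time.

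Much of this stands. A first-dose rule cannot be excluded, the paracetamol parallel proves little, and the other safeguards limit the consequence. But the protocol nowhere states a first-dose rule or links these episodes to observation time. It places them usually within 48 hours of vaccination, a period that neither 15 nor 30 minutes covers, and it gives acute and anaphylactic reactions as the reason for the watch. The Visit 1 exception is also worded by product. The mismatch therefore remains on the face of the document.

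**Conclusion.** The concern holds as a minor inconsistency in a safety procedure. Observation after Comvac5 is 30 minutes at dose 1 and 15 minutes at dose 2, for up to 57 infants, with no stated reason. The textual difference is certain. That it is an omission is likely but not proven. No harm is shown, and the primary endpoint, sample size and analysis are unaffected. The conclusion does not depend on whether Visit 3 takes place at home.

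**What to change.** Amend 9.5.3 item 13 to carry the same exception as Visit 1: 15 minutes, or 30 minutes for infants who received Comvac5. If the sponsor and the investigator intend the longer watch for the first dose only, the protocol should say so and give the clinical reason. That choice is theirs, but the precautionary course is to restore 30 minutes.

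The cost is one line of protocol text, any matching visit worksheet, and 15 more minutes per wP infant at Visit 3 (at most 14.25 hours in total). No analysis change is needed.

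Timing matters. This version is dated December 2023 and the planned study period ends in June 2024. From Visit 3 (4 months) to Visit 7 (13 months) is 13 - 4 = 9 months. An infant finishing by June 2024 would therefore have had Visit 3 by about September 2023. If Visit 3 is indeed complete for everyone, the amendment can no longer change conduct. The trial report should then state the observation time actually applied after the second Comvac5 dose.

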## 9.5.2 Visit 2: 7 days after V1 (range 7-14 days)

1. Check inclusion and exclusion criteria if still valid

2. Review eDiary or paper diary for AEs/SAEs since last visit

3. Record and report AEs/SAEs that occurred since last visit

4. Record paracetamol and/or ibuprofen use in 72h prior to immunisation.

5. Measure and record the participant axillary temperature

6. Administer 0.5ml dose of 4CMenB by intra-muscular injection into the left antero-lateral thigh, record site and time of vaccination and batch number in source document and in red book

7. After explanation according to JCVI recommendations, parents would be advised to give 2.5 mls of paracetamol (120mg/5ml) orally immediately after vaccination, and 2 other doses 4-6hours apart after last dose.

8. Observe the participant for 15 minutes after vaccination for any significant acute reactions, with appropriate medical treatment readily available in case of anaphylactic reaction. Any AEs occurring during the observation period should be recorded in the source document

9. Instruct parent/legal guardians to contact the study team immediately should they manifest any signs/ symptoms they perceive as serious or if the child is admitted overnight to hospital.

10. Leave with parents/guardians anaesthetic cream (unless spray to be used), dressing pads and instructions for blood test visit if not given previously

11. Schedule next visit

12. Study staff complete red book, paperwork in the case of no direct data entry and enter onto database

## 9.5.3 Visit 3: 56 days post V1 (+14 days)

1. Check Inclusion/ exclusion criteria are still valid

2. Review eDiary or paper diary for AEs/SAEs and prescription medicine since the last visit

3. Record and report any AEs/SAEs that have occurred since the last visit.

4. Issue new eDiary or paper diary and remind parents to measure and record temperature, local and systemic reactions, AEs (for 7 days post any vaccination) and concomitant medications (for 28 days post vaccination).

5. Measure and record axillary temperature

6. Administer 0.5ml DTaP-IPV-Hib-Hep B by intra-muscular injection into the upper right anterolateral thigh (aP group), record in source document and in red book

7. Administer 0.5ml DTwP-Hib-Hep B by intra-muscular injection into the upper right antero-lateral thigh (wP group), record in source document and in red book

8. Administer 0.5ml PCV by intra-muscular injection into the upper left antero-lateral thigh record in source document and in red book

9. Administer 0.5ml IPV by intra-muscular injection into the lower left antero-lateral thigh (wP aroup), record in source document and in red book

10. Administer Rotavirus vaccine oral drops

11. Issue the parents/ legal guardian with a continuous temperature-monitoring device, together with instructions. Fit on the child and demonstrate how to fit, check function

12. Check parent familiar with how to measure and record temperature, local and systemic reactions, AEs (for 7 days post any vaccination) and concomitant medications (for 28 days post vaccination).

13. Observe the participant for 15 minutes after vaccination for any significant acute reactions, with appropriate medical treatment readily available in case of anaphylactic reaction. Any AEs occurring during the observation period should be recorded in the source document

14. Issue (only if parent's do not have any) and provide instructions on the use of paracetamol prophylaxis to those whose infant is randomised to receive wP

15. Instruct parent/legal guardians to contact the study team immediately should they manifest any signs/ symptoms they perceive as serious or if the child is admitted to the hospital.

16. Leave with parents/guardians anaesthetic cream (unless spray to be used), dressing pads and instructions for blood test visit if not given previously.

17. Schedule next visit

18. Study staff complete red book, paperwork in case of no direct data entry and enter onto database

## 9.5.4 Visit 4: 7 days after V3 (range 7-14 days)

- 1. Check inclusion and exclusion criteria if still valid
- 2. Review eDiary or paper diary for AEs/SAEs since last visit
- 3 Record and report AEs/SAEs that occurred since last visit
- 4. Record paracetamol and/or ibuprofen use in 72h prior to immunisation.
- 5. Measure and record the participants axillary temperature

6. Administer 0.5ml dose of 4CMenB by intra-muscular injection into the left antero-lateral thigh, record site and time of vaccination and batch number in source document and in red book

7. After explanation according to JCVI recommendations, parents would be advised to give 2.5 mls of paracetamol (120mg/5ml) orally immediately after vaccination, and 2 other doses 4-6 hours apart after last dose.

8. Observe the participant for 15 minutes after vaccination for any significant acute reactions, with appropriate medical treatment readily available in case of anaphylactic reaction. Any AEs occurring during the observation period should be recorded in the source document

9. Instruct parent/legal guardians to contact the study team immediately should they manifest any signs/ symptoms they perceive as serious or if the child is admitted to the hospital.

10. Leave with parents/guardians anaesthetic cream (unless spray to be used), dressing pads and instructions for blood test visit if not previously given.

- 11. Schedule next visit
- 12. Study staff complete, red book, paperwork and enter onto database

## 9.5.5 Visit 5: 28 days post V4 (+ 14 days) (all participants)

1. Check Inclusion/ exclusion criteria are still valid

- 2. Review eDiary or paper diary for AEs/SAEs and prescription medicine since the last visit
- 3. Record and report any AEs/SAEs that have occurred since the last visit.
- 4. Measure and record axillary temperature
- 5. Blood sampling: obtain up to 4 mls
- 6. Collect Mucosal Lining Fluid (MLF) using synthetic absorptive matrices (SAM)

7. Instruct parent/legal guardians to contact the study team immediately should they manifest any signs/ symptoms they perceive as serious or if the child is admitted to the hospital.

8. Parents informed of parental motivation and satisfaction survey questionnaire link that will be sent to them before the V6 visit.8. Schedule next visit

9. Leave with parents/guardians anaesthetic cream (unless spray to be used), dressing pads and instructions for blood test visit (V6).

10. Complete paperwork in case of no direct data entry and enter onto database

#### 9.5.6 Visit 6: 12 months +14 days (all participants)

1. Check Inclusion/ exclusion criteria are still valid

2. Review eDiary or paper diary for AEs/SAEs and prescription medicine since the last visit

3. Record and report any AEs/SAEs that have occurred since the last visit.

4. Issue new eDiary or paper diary and remind parents to measure and record temperature, local and systemic reactions, AEs (for 7 days post any vaccination) and concomitant medications (for 28 days post vaccination).

5. Measure and record axillary temperature

6. Blood sampling: obtain up to 6 mls

7. Collect Mucosal Lining Fluid (MLF) using synthetic absorptive matrices (SAM)

8. Administer 0.5ml DTaP-IPV-Hib-Hep B by intra-muscular injection into the upper right anterolateral thigh record in source document and in red book

9. Administer 0.5ml PCV by intra-muscular injection into the upper left antero-lateral thigh record in source document and in red book

10. Explain how to measure and record temperature, local and systemic reactions, AEs (for 7 days post any vaccination) and concomitant medications (for 28 days post vaccination).

11. Issue the parents/ legal guardian with a continuous temperature-monitoring device, together with instructions. Fit on the child and demonstrate how to fit, check function and remove device

12. Observe the participant for 15 minutes after vaccination for any significant acute reactions, with appropriate medical treatment readily available in case of anaphylactic reaction. Any AEs occurring during the observation period should be recorded in the source document

13. Instruct parent/legal guardians to contact the study team immediately should they manifest any signs/ symptoms they perceive as serious or if the child is admitted to the hospital.

14. Leave with parents/guardians anaesthetic cream (unless spray to be used), dressing pads and instructions for next blood test visit (V7).

15. Schedule next visit

16. Study staff complete, paperwork in case of no direct data entry and enter onto database

